1.2. Study Design

Study KDAF is a Phase 2b, randomized, double-blind, placebo-controlled study to determine the appropriate dose and dosing frequency of peresolimab in adult participants with moderately-to-severely active RA.

[figure not shown]
This study includes a

- Period 1: screening period occurring approximately 1 to 42 days prior to Period 2
- Period 2: 12-week double-blind, placebo-controlled treatment period
- Period 3: 48-week double-blind treatment period, and
- Period 4: posttreatment follow-up period occurring 4 and 12 weeks from last treatment period visit (Week 60) or Early Discontinuation Visit.

See the Schedule of Activities (SoA) in the protocol for visit schedule, procedural and assessment details.

In the remainder of this statistical analysis plan (SAP), the first 12 weeks in Period 3 (that is, Weeks 12 to 24) will be referred as Period 3A and the last 36 weeks in Period 3 (that is, Weeks 24 to 60) as Period 3B for an analysis purpose. Combined Periods 2 and 3 will be referred as the Treatment Period (Weeks 0 to 60).

Figure KDAF.1.1 describes the study design for the treatment periods (Periods 2 and 3).

[figure not shown]

Abbreviations: CDAI = Clinical Disease Activity Index; SC = subcutaneous injection; Q4W = every 4 weeks; Q12W = every 12 weeks.

Note: At Week 12, participants receiving placebo Q4W will begin receiving either 400 mg or 1000 mg peresolimab Q4W. At Week 24, participants receiving 400 mg or 1000 mg peresolimab Q4W may be switched to Q12W dosing following assessment of CDAI scores.

Figure KDAF.1.1 Study design.

Participant population

Treatment period design

- 100 mg of peresolimab every 4 weeks (Q4W)
- 400 mg of peresolimab Q4W
- 1000 mg of peresolimab Q4W
- placebo Q4W up to Week 12 followed by 400 mg of peresolimab Q4W, and
- placebo Q4W up to Week 12 followed by 1000 mg of peresolimab Q4W.

Participants randomly assigned to placebo Q4W at Week 0

At Week 12, participants receiving placebo Q4W will begin receiving either 400 mg or 1000 mg peresolimab Q4W based on randomization at Week 0. Treatment assignment will be blinded, and the participants will continue their assigned peresolimab dose and dosing frequency until the end of the study.

Participants randomly assigned to 100 mg peresolimab at Week 0

Participants receiving 100 mg peresolimab will continue their assigned dose and dosing frequency throughout the duration of the treatment period. No changes will occur.

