In an AE overview table, the number and percentage of patients in the safety analysis set who experienced death, a serious adverse event (SAE), any TEAE, permanent discontinuation from study drug due to an AE, or a severe TEAE will be summarized by treatment group.

The number and percentage of patients with TEAEs will be summarized by treatment group in 2 formats listed below. For events that are gender specific, the denominator and computation of the percentage will only include patients from the given gender.

- By MedDRA PT nested within SOC with SOCs ordered alphabetically, and events ordered within each SOC by decreasing frequency in the 1000 mg of peresolimab Q4W treatment group
- By MedDRA PT with events ordered by decreasing frequency in the 1000 mg of peresolimab Q4W treatment group

AEs leading to permanent discontinuation of study drug and AEs leading to temporary interruption of study drug will also be summarized by treatment group using MedDRA PT nested within SOC. AE leading to temporary interruption of study drug will be identified using the response of "Drug Interrupted" in the question "What action taken with study treatment?" on the *Adverse Event* eCRF. Events will be ordered by decreasing frequency within SOC in 1000 mg of peresolimab Q4W treatment group.

A summary of temporary interruptions of study drug due to AEs will also be provided, showing the number of patients who experienced at least 1 temporary interruption and the number of temporary interruptions per patient with an interruption. Further, the duration of each temporary interruption (in days) and the cumulative duration of dose interruption (in days) using basic descriptive statistics (n, mean, SD, minimum, first quartile, median, third quartile, and maximum) will be displayed. Duration of study drug interruption will be calculated as: visit date of the missed dose – date of next resumed dose + 1, only if both dates are provided.

The number and percentage of patients with TEAEs will be summarized by maximum severity, SOC and PT by treatment using MedDRA PT ordered by decreasing frequency for the TEAEs. For each patient and TEAE, the maximum severity for the MedDRA level being displayed is the maximum postbaseline severity observed from all associated LLTs mapping to that MedDRA PT.

Adverse events of special interest include hypersensitivity, injection site reactions, infections, and malignancy.

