4.6.2.2. Allergic Reactions and Hypersensitivities

The current standard MedDRA Standardized Medical Queries (SMQs) to search for relevant events will be used. TEAEs are characterized as follows:

- Anaphylactic reaction SMQ (20000021)
- Hypersensitivity SMQ (20000214)
- Angioedema SMQ (20000024).

The frequency and percentage of patients experiencing treatment-emergent hypersensitivities will be summarized by treatment arm, SMQ, and PT during the Treatment Period. The frequency and percentage of patients experiencing treatment-emergent hypersensitivities will also be summarized by treatment arm and timing category.

Exposure-adjusted incidence rates (per 100 PYs) of treatment-emergent hypersensitivities will be summarized.

Total number of patients who experienced the TEAE for each PT while they were on Peresolimab will be divided by the sum of all patients' time (in 100 years) of Peresolimab

exposure during the treatment period. The entire time on the study during the Peresolimab treatment period will be used to calculate the patient's time of exposure.

The time to onset of first treatment-emergent hypersensitivity during the Treatment Period and the duration of each treatment-emergent hypersensitivity during the Treatment Period will also be defined and calculated in the same way.

A by-patient listing of all treatment-emergent hypersensitivities will be provided.

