A listing of patients with detectable hepatitis B virus (HBV) DNA will be provided.

HBV DNA status (not detectable, detectable but not quantifiable [that is, <lower limit of detection (LLOD)], quantifiable [that is, ≥LLOD]) will be summarized, stratified by applicable baseline HBV serology status.

A summary table of herpes zoster will be provided, including event maximum severity, seriousness, whether resulting in temporary study drug interruption, whether resulting in study drug discontinuation, and event outcome. See Appendix 10 (Section 6.10) for PT list for herpes zoster.

A summary table of herpes simplex will be provided, including event maximum severity, seriousness, whether resulting in temporary study drug interruption, whether resulting in study drug discontinuation, and event outcome. See Appendix 10 (Section 6.10) for PT list for herpes simplex.

The time to onset of first treatment-emergent infectious AE during the Treatment Period will be defined as follows:

```
Time to onset of first treatment-emergent infectious AE (in weeks) = (Start\ date\ of\ first\ infectious\ AE - Date\ of\ first\ injection\ +1)/7.
```

Note that if an infectious AE was preexisting prior to the date of first injection and subsequently became treatment-emergent due to worsening post-baseline, the date of worsening will be used in place of the AE start date.

If a patient does not have a treatment-emergent infectious AE during the Treatment Period, they will be censored at the date of completion or ED from the Treatment Period. Kaplan-Meier estimates of the proportion of patients not yet experiencing their first treatment-emergent infectious AE at 12, 24, 36, 48, and 60 weeks will be provided for each treatment arm. A Kaplan-Meier plot of the time to onset will be presented by treatment arm.

The duration of each treatment-emergent infectious AE during the Treatment Period will be defined as follows:

```
Duration of treatment-emergent infectious AE (in weeks) = (End date of AE – Start date of AE + 1) / 7.
```

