If an AE has not ended by the date of completion or ED from the study, including the Posttreatment Follow-up Period, it will be censored as of that date. Descriptive statistics for the duration of treatment-emergent infectious AEs will be summarized by treatment arm. If a patient has more than 1 treatment-emergent infectious AE during the Treatment Period, then each AE will contribute to the analysis. If a patient does not have a treatment-emergent infectious AE during the Treatment Period, they will not be included in the analysis.

A by-patient listing of treatment-emergent infections will be provided.

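### Infection durations cut off at study end enter ordinary descriptive statistics, so on the plain reading of the SAP mean duration is understated, mainly for long infections

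*SAP*

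**What the plan says.** SAP 4.6.2.4 (Infections) defines the duration of each treatment-emergent infection in weeks as end date minus start date plus 1 day, divided by 7. For events without an end date it adds: "If an AE has not ended by the date of completion or ED from the study, including the Posttreatment Follow-up Period, it will be censored". The summary is stated next: "Descriptive statistics for the duration of treatment-emergent infectious AEs will be summarized by treatment arm". Where a patient has several infections, "then each AE will contribute to the analysis".

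For a different quantity, time to first infection, the same section plans "Kaplan-Meier estimates of the proportion of patients not yet experiencing their first treatment-emergent infectious AE", with a plot by arm. That method is not carried over to duration.

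The infection section does not list which descriptive statistics it means. Where the SAP does spell them out, for dose interruptions in 4.6.2, they are "basic descriptive statistics (n, mean, SD, minimum, first quartile, median, third quartile, and maximum".

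SAP 4.6.2.2 (Allergic Reactions and Hypersensitivities) says that "the duration of each treatment-emergent hypersensitivity during the Treatment Period will also be defined and calculated in the same way", without naming the section it points to.

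**The concern.** Calling a time censored changes nothing unless the estimator uses that status. For an event still ongoing at study end, the recorded time is a lower bound on its duration. If that bound goes into a mean with the completed durations, the mean is too low. The shortfall falls on the longest events, because they are the ones most likely to be cut off.

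Infections are adverse events of special interest in this SAP, and the section covers opportunistic infections and reactivation of tuberculosis or hepatitis, where long courses are possible. Durations are shown by arm, so if one arm loses more participants soon after an infection, its infections would appear to clear faster for that reason alone.

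**Working it through.** The plan states no figure for duration or for the number of ongoing events, so there is nothing of its own to reproduce. The check has two parts: direction, which needs no assumptions about the distribution, and size, which does.

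**Direction.** Let D be the true duration and C the time from onset to the end of that participant's study. The recorded time is T = min(D, C). T never exceeds D, so no cut-off event is overstated. The shortfall, D - C when D > C, grows with D.

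**Inputs for size**
- From SAP 1.2: treatment runs to Week 60, with a "posttreatment follow-up period occurring 4 and 12 weeks from last treatment period visit (Week 60) or Early Discontinuation Visit". A completer is therefore followed to about Week 72.
- Assumed: onset uniform over Weeks 0-60, so C is uniform on 12 to 72 weeks.
- Assumed: D exponential with mean m = 2, 8 or 26 weeks.
- Assumed: nobody leaves early, or 20% leave at a time uniform on 0-8 weeks after onset.

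**Formula.** For exponential D and independent C, E[T] = m × (1 - E[exp(-C/m)]). The relative bias in the mean is minus E[exp(-C/m)], which is also the proportion of events still ongoing.

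**No early leavers.** The bias is -A, where A = (m/60) × (exp(-12/m) - exp(-72/m)).
- m = 2: A = 0.0001, so about 0%.
- m = 8: A = 0.1333 × (0.2231 - 0.0001) = 0.030, so -3%. The plain mean is about 7.8 weeks.
- m = 26: A = 0.4333 × (0.6303 - 0.0627) = 0.246, so -25%. The plain mean is 19.6 weeks.

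**20% leave and skip all follow-up.** For leavers the corresponding term is B = (m/8) × (1 - exp(-8/m)), and the bias is -(0.8A + 0.2B).
- m = 2: B = 0.245, so -4.9%.
- m = 8: B = 0.632, so -(0.024 + 0.126) = -15%. The plain mean is 6.8 weeks.
- m = 26: B = 0.861, so -(0.197 + 0.172) = -37%. The plain mean is 16.4 weeks.

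**20% leave but complete the 12-week follow-up.** Each leaver gains 12 weeks, so B is multiplied by exp(-12/m).
- m = 2: about 0%.
- m = 8: -(0.024 + 0.2 × 0.632 × 0.223) = -5.2%.
- m = 26: -(0.197 + 0.2 × 0.861 × 0.630) = -30.5%.

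Capping leavers' follow-up at Week 72, checked by simulation, moves the last two only to -5.3% and -30.6%, with plain means of 7.6 and 18.0 weeks.

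| True mean (weeks) | No early leavers | 20% leave, follow-up completed | 20% leave, follow-up skipped |
|---|---|---|---|
| 2 | 0% | 0% | -5% |
| 8 | -3% | -5% | -15% |
| 26 | -25% | -31% | -37% |

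**Median.** At m = 8 the true median is 8 × ln 2 = 5.55 weeks. The plain median is also 5.55 with no leavers, and unchanged when leavers complete follow-up. At m = 26 with no leavers, the plain median is about 16.2 against a true 18.0.

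**Where the loss falls.** In a simulation of 400,000 events with m = 12 and no leavers, the longest tenth averages 39.5 weeks in truth and 32.0 as recorded. The other nine tenths average 8.92 and 8.78.

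**Does a censoring-aware method recover the truth?** At m = 26 with no leavers, the simulated Kaplan-Meier median is 18.3 against 18.0, and total time divided by resolved events is 26.0 weeks. Dropping ongoing events is no remedy: resolved events alone average 15.8 weeks, lower than the plain mean of 19.6.

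**The case against.** **The SAP says censored, and Kaplan-Meier quartiles are descriptive statistics too.** This is fair. Nowhere does the SAP say that cut-off times are averaged as completed durations, and a reader who infers that it does goes beyond the text. But Kaplan-Meier is named for onset and not for duration, every event contributes, and no other handling is given. A programmer following the text would compute ordinary statistics on the cut-off times.

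**Hypersensitivity.** A reader might infer that hypersensitivity durations are understated as well. That takes two inferences. SAP 4.6.2.2 refers to an unnamed definition, and it sets out neither a censoring rule nor a summary of duration. The infection rule is the likely referent, because no duration is defined earlier in that section, but the documents do not establish the bias there.

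**Early leaving.** The largest figures need leavers who skip all follow-up, and the documents point the other way. SAP 1.2 places follow-up visits after early discontinuation, and the censoring rule includes that period. Protocol 7.1 encourages those who stop study drug to stay for all remaining visits, Protocol 7.1.3 has drug withheld for infection, and Protocol 7.2 expects discontinuation to be uncommon. No document supports 20%. This objection stands, and the skipped-follow-up column is an upper case only.

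**Most infections are short.** Also fair: at a true mean of 2 weeks with follow-up completed, the bias is nil. A 26-week mean across all infections in an arm is an extreme setting.

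**Other safeguards.** By-patient listings of infections are planned, and event outcome is tabulated for herpes zoster and herpes simplex. Protocol 8.3 has events of special interest followed to resolution or stabilization. These help a careful reader, but the duration rule still stops at study end and the infection section plans no count of ongoing events.

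**Conclusion.** The concern holds in a limited form. Followed as written, the SAP puts the shorter of true duration and time to study end into ordinary descriptive statistics, and the mean of that quantity can only be too low. The direction is certain on this reading.

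The size is not known from the documents. With follow-up completed and the assumptions above, the bias in the mean runs from nil for 2-week infections, through 3% to 5% at 8 weeks, to 25% to 31% at 26 weeks. The plain median is essentially unaffected at 8 weeks.

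A distortion between arms is possible if leaving rates differ: at a true mean of 26 weeks, an arm with no leavers would show 19.6 weeks and an arm with 20% leaving but followed would show 18.0. The documents give no reason to expect such a difference, and Table KDAF.3.1 plans no between-treatment comparison for the combined Treatment Period.

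This affects a descriptive safety summary only. The primary endpoint, the error rate and the sample size are untouched.

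**What to change.** In SAP 4.6.2.4, state that duration is summarized per arm by the Kaplan-Meier median and quartiles, with unresolved events censored at the last study date. Beside it, report the number and percentage of events ongoing at last contact, by arm. That count is needed because Kaplan-Meier assumes that leaving is unrelated to how long the infection will last; if people leave because an infection persists, Kaplan-Meier is biased too. Since a patient may contribute several events, any confidence interval should allow for clustering within patient.

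In SAP 4.6.2.2, name the section whose definition is meant, and apply the same method if hypersensitivity duration is summarized.

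The cost is a sentence or two in the SAP and a changed table shell. No new data are needed. Reported durations would lengthen little for acute infections and more for long ones.

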4.6.2.5. Malignancies

Malignancies will be defined using terms from the Malignant tumors SMQ (20000194) or Malignancies SMQ (20000090).

The frequency and percentage of patients with a treatment-emergent malignancy will be summarized by treatment arm, maximum severity, SOC, and PT during the Treatment Period. Exposure-adjusted incidence rates (per 100 PYs) for each type of treatment-emergent malignancy will be presented by treatment arm, and PT during the Treatment Period. AEs will be summarized under a particular time interval if they started or worsened on or after the interval start date and before the interval end date.

Malignancies excluding nonmelanoma skin cancers (NMSC) and NMSC will be also reported separately. NMSC will be defined using the below PTs:

- Squamous cell carcinoma of skin (10041834)
- Bowen's disease (10006059)
- Basal cell carcinoma (10004146)
- Basosquamous carcinoma (10004178)
- Basosquamous carcinoma of skin (10004179)
- Squamous cell carcinoma (10041823)
- Skin squamous cell carcinoma metastatic (10077314)
- Skin cancer (10040808)
- Carcinoma in situ of skin (10007390)
- Keratoacanthoma (10023347)
- Vulvar squamous cell hyperplasia (10079905)
- Skin squamous cell carcinoma recurrent (10081136)
- Lip squamous cell carcinoma (10064055)
- Penile Squamous cell carcinoma (10059631)

The time to onset of first treatment-emergent malignancies during the Treatment Period will be summarized in the same way as time to onset of first treatment-emergent infections.

A by-patient listing of treatment-emergent malignancies will be provided.

Additional information will be provided in the Adjudication Committee Charter.

4.6.2.6. Depression

Depression will be defined using terms from the Depression and suicide/self-injury SMQ (20000035).

The frequency and percentage of patients with treatment-emergent depression will be summarized by treatment arm, maximum severity, SOC, and PT during the Treatment Period. Exposure-adjusted incidence rates (per 100 PYs) for each type of treatment-emergent depression will be presented by treatment arm, PT, and time interval during the Treatment Period. AEs will be summarized under a particular time interval if they started or worsened on or after the interval start date and before the interval end date.

A by-patient listing of treatment-emergent depression will be provided.

4.6.2.7. Suicide-related Thoughts and Behaviors

Suicide-related ideations and behaviors, based on Columbia Suicide Severity Rating Scale (C-SSRS), will be summarized by treatment arm separately for patients who completed the C-SSRS starting at enrollment versus patients who were already enrolled when the C-SSRS was introduced to the study during the Treatment Period.

Treatment-emergent suicide-related ideations and behaviors during the Treatment Period are defined as any ideation or behavior reported after the baseline visit (Visit 2) and on or prior to Visit 18 (Week 60) or ED. The frequency and percentage of patients with treatment-emergent

suicide-related ideations and behaviors will be summarized by treatment arm for patients who completed the C-SSRS starting at enrollment by C-SSRS category (1 through 10), by type (ideation or behavior), and overall during the Treatment Period.

Suicide-related ideations and behaviors will be listed by patient and visit separately for patients who completed the C-SSRS starting at enrollment versus patients who were already enrolled when the C-SSRS was introduced to the study. Only patients that show suicidal ideation/behavior will be displayed, including lifetime history at screening. If patient's answers are all 'no' for the C-SSRS, then that patient will not be displayed. However, if a patient reported any ideation or behavior at any time point, then all their ideation and behavior will be displayed, even if not positive.

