8.2.6. Suicidal Ideation and Behavior Risk Monitoring

Participants should be monitored appropriately and observed closely for suicidal ideation and behavior or any other unusual changes in behavior. Participants who experience signs of suicidal ideation and behavior should undergo a risk assessment. All factors contributing to suicidal

ideation and behavior should be evaluated and consideration should be given to discontinuation of the study intervention.

Baseline assessment of suicidal ideation and behavior and intervention emergent suicidal ideation and behavior will be monitored during the study using the C-SSRS.

C-SSRS

The C-SSRS is a scale that captures the occurrence, severity, and frequency of suicidal ideation and behavior during the assessment period via a questionnaire. The scale was developed by the National Institute of Mental Health trial group (TASA) for the purpose of being counterpart to the Columbia Classification Algorithm of Suicide Assessment (C-CASA) categorization of suicidal events.

For this study, the C-SSRS is adapted for the assessment of the ideation and behavior categories only. The Intensity of Ideation and Lethality of Behavior sections are removed.

Nonleading AE collection should occur prior to the collection of the C-SSRS.

If a suicide-related event is discovered *during the C-SSRS* but was not captured during the nonleading AE collection, sites should not change the AE form, except if a serious AE occurs or an AE leading to discontinuation occurs.

If a serious AE occurs, then capture the AE on the AE form and follow the process for reporting SAEs.

If an AE leads to discontinuation, then capture the AE on the AE form and record the reason for discontinuation.

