> A medicinal product used for the needs of a clinical study as described in the protocol, but not as an investigational medicinal product. Examples include rescue medication, challenge agents, agents to assess endpoints in the clinical study, or background

treatment.

NRS Numeric rating scale

NSAIDs nonsteroidal anti-inflammatory drugs

Participant Equivalent to CDISC term "subject": an individual who participates in a clinical study,

either as recipient of an investigational medicinal product or as a control

PaGADA Patient's Global Assessment of Disease Activity

PhGADA Physician's Global Assessment of Disease Activity

PC product complaint

PD-1 programmed cell death protein 1

PK/PD pharmacokinetics/pharmacodynamics

PPD Purified protein derivative

PRO/ePRO patient-reported outcomes/electronic patient-reported outcomes

PT-INR prothrombin time/international normalized ratio

CCI

RA Rheumatoid arthritis

CCI

SAE serious adverse event

SAP statistical analysis plan

CCI

Screen The act of determining if an individual meets minimum requirements to become part of

a pool of potential candidates for participation in a clinical study.

SDAI Simplified Disease Activity Index

SF-36 Short Form-36 version 2 health survey acute form

Syollen Joint Counts

SUSAR suspected unexpected serious adverse reaction

TBL Total bilirubin level

TEAE Treatment-emergent adverse event: An untoward medical occurrence that emerges

during a defined treatment period, having been absent pretreatment, or worsens relative to the pretreatment state, and does not necessarily have to have a causal relationship

with this treatment.

TJC Tender Joint Counts

TSJC Tender Joint Counts and Swollen Joint Counts

TST Tuberculin skin test

ULN upper limit of normal

VAS Visual analog scale

WHO World Health Organization

WOCBP Women of childbearing potential

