4.6.2. Adverse Events

AEs are recorded in the eCRF. Each AE will be coded to System Organ Class (SOC) and Preferred Term (PT), using the *Medical Dictionary for Regulatory Activities* (MedDRA) version that is current at the time of database lock. Severity of AEs is recorded as mild, moderate, or severe.

A treatment-emergent adverse event (TEAE) is defined as an event that first occurred or worsened in severity after baseline and on or prior to the earliest of the visit study drug disposition dates or the last visit date during the treatment period, whichever occurred first, and up to 50 days after study treatment discontinuation. Baseline for Period 2 is defined as all preexisting conditions recorded at Visit 1 and any AEs recorded before the first dose of study intervention. Baselines for other periods are defined as unresolved AEs just prior to the first dose of each period. The MedDRA Lowest Level Term (LLT) will be used in defining which events

are treatment-emergent. The maximum severity for each LLT will be used as baseline. If an event is preexisting during the baseline period for Period 2, but it has missing severity, and the event persists during the treatment period or up to 50 days after treatment discontinuation, then the baseline severity will be considered mild for determining any postbaseline treatment-emergence (that is, the event is treatment-emergent unless the severity is coded mild at postbaseline). If an event occurring postbaseline has a missing severity rating, then the event is considered treatment-emergent. Should there be insufficient data for an AE start date to make this comparison (for example, the AE start year is the same as the treatment start year, but the AE start month and day are missing), the AE will be considered treatment-emergent. For events occurring on the day of the first dose of study treatment, Week 0 (V2) in most cases, the events will be assumed to occur posttreatment and considered as TEAE. For events occurring on the day of doses except for the first dose of study treatment, the events will be considered to occur prior to the study drug injection.

In general, summaries will include the number of patients in the safety population (N), frequency of patients experiencing the event (n), and relative frequency (that is, percentage; n/N*100).

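### Treatment-emergent suicidal ideation or behavior is defined without comparison to the pre-treatment C-SSRS, so unchanged pre-existing ideation is counted as emergent in every arm

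*SAP*

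**What the plan says.** SAP 4.6.2.7 gives the rule: treatment-emergent suicide-related ideation and behavior is "defined as any ideation or behavior reported after the baseline visit (Visit 2", with the window closing at Visit 18 (Week 60) or early discontinuation. Counts and percentages are tabulated by arm for participants who "completed the C-SSRS starting at enrollment by C-SSRS category (1 through 10), by type (ideation or behavior), and overall during the Treatment Period". The same section plans a by-patient, by-visit listing: "Only patients that show suicidal ideation/behavior will be displayed, including lifetime history at screening". Once a participant has any positive answer, all of that participant's answers are listed, negative ones included.

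Protocol 8.2.6 treats the pre-treatment state and the on-treatment state as two things to observe: "Baseline assessment of suicidal ideation and behavior and intervention emergent suicidal ideation and behavior will be monitored during the study using the C-SSRS".

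Elsewhere in the plan the term carries a comparison. SAP 4.6.2 says: "A treatment-emergent adverse event (TEAE) is defined as an event that first occurred or worsened in severity after baseline". The TEAE entry in Protocol Appendix 10 describes an event that emerges during treatment, "having been absent pretreatment, or worsens relative" to the state before treatment. SAP 4.6.3 (laboratory) and SAP 4.6.5 (vital signs) count a result as treatment-emergent only if the participant was within limits at every baseline visit.

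**The concern.** Within one safety section the same label has two meanings. For adverse events, laboratory results and vital signs it means a change from the pre-treatment state. For the C-SSRS it means any report after Visit 2. The C-SSRS table is therefore a count of participants with any post-baseline report, under a heading that tells the reader something new has appeared.

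The information needed for the comparison should be available. The table is limited to participants who completed the C-SSRS from enrollment, who are the ones expected to have pre-treatment answers. The definition does not use those answers.

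At stake is how a small safety table reads. Suicidality counts may be low, and a few participants with unchanged ideation could then make up a noticeable share of them. Adding such participants to every arm also makes a real difference between arms harder to see.

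**Working it through.** The plan states no figure that depends on this definition, so there is nothing to reproduce. The check sets the rules side by side, then gives an illustration of size.

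**Step 1: what each rule requires.**

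| Outcome | Source | Comparison with the pre-treatment state? |
|---|---|---|
| Adverse events | SAP 4.6.2; Protocol 9.3.5 and Appendix 10 | Yes: first occurrence or worsening |
| Laboratory results | SAP 4.6.3 | Yes: within limits at all baseline visits |
| Vital signs | SAP 4.6.5 | Yes: within limits at all baseline visits |
| C-SSRS | SAP 4.6.2.7 | No: any report after Visit 2 |

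SAP 4.1 defines a safety baseline by period, but the C-SSRS definition does not use it. No other visible section supplies a baseline condition for the C-SSRS.

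**Step 2: how example participants are classified.** Here a is any ideation category and b is a higher one.

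| Recent pre-treatment | After Visit 2 | SAP 4.6.2.7 | New-or-worse rule |
|---|---|---|---|
| None | a | Emergent | Emergent |
| a | b (worse) | Emergent | Emergent |
| a | a (unchanged) | Emergent | Not emergent |
| b | a (improved) | Emergent | Not emergent |
| None recent, a in the remote past | a | Emergent | Emergent if the look-back is recent; not emergent if it is lifetime |

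The third and fourth rows are the error. The last row shows why any correction must state its look-back.

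**Step 3: illustration of size.** Group sizes are from SAP Section 5: about 60 on 100 mg, 120 on 400 mg, 120 on 1000 mg and 120 on placebo (60 + 120 + 120 + 120 = 420). Let p be the proportion with pre-existing, unworsened ideation that is reported again after Visit 2. The documents do not give p; 0% to 5% is assumed. Zero is included because exclusion criteria before number 20 are not visible, so an exclusion for suicidality may or may not exist.

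Mislabelled participants = group size × p:

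- group of 120: 120 × 0 = 0 to 120 × 0.05 = 6
- group of 60: 60 × 0 = 0 to 60 × 0.05 = 3
- all participants: 420 × 0 = 0 to 420 × 0.05 = 21

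Under a new-or-worse rule these participants contribute 0.

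**The case against.** **The definition is explicit and sensitive.** Counting every post-baseline report misses nothing, and for a safety screen that has value. This stands as a reason to keep the count, but not as a reason to call it treatment-emergent.

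**The C-SSRS is not an adverse event form, so the TEAE rule need not govern it.** This is correct as far as it goes. Suicide-related adverse events are analyzed separately through the depression and suicide/self-injury query in SAP 4.6.2.6. However, Protocol 8.2.6 keeps events found only through the C-SSRS off the adverse event form unless they are serious or lead to discontinuation, so that route does not replace this table. The laboratory and vital-sign rules are not adverse event rules either, and they do compare with baseline.

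**A reader might infer that worsening cannot be told from persistence.** The documents do not support that. The listing shows screening history and every answer by visit for anyone with a positive response. With few cases, a reader can sort them by hand. The limitation is in the summary table.

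**A reader might infer that the rule biases the results against peresolimab.** It does not do so by itself, because it applies equally to every arm. SAP 4.6 also calls for safety summaries by period, and Period 2 has a pooled placebo group. It is true that SAP 4.6.2.7 refers to the Treatment Period (Weeks 0 to 60), for which Table KDAF.3.1 lists only groups that include peresolimab. That follows from moving placebo participants to peresolimab at Week 12. It affects every Weeks 0 to 60 safety table and would remain under a corrected definition.

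**Conclusion.** The point holds as a defect of definition. SAP 4.6.2.7 states a rule which, followed literally, places unchanged or improved pre-existing ideation in a treatment-emergent table, contrary to the meaning the plan gives that term elsewhere. The table is descriptive, no hypothesis test depends on it, and the listing mitigates the problem.

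The size is not known. On an assumed 0% to 5% with unworsened ideation reported again, it is about 0 to 6 participants per group of 120 and 0 to 3 in the group of 60. A reader might want to turn this into a factor by which the true count is inflated. That would need rates of baseline ideation, persistence and new onset, none of which is in the documents, and the number affected could be close to zero. C-SSRS visit timing is not visible either, so nothing can be said about any particular post-baseline visit.

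**What to change.** In SAP 4.6.2.7:

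1. Define treatment-emergent ideation as a post-baseline category that is new or higher than the maximum category in a stated recent pre-treatment look-back. Use screening/baseline recall and not lifetime history. With a lifetime maximum as the reference, remote past ideation would cancel a genuine recurrence on treatment.
2. Define treatment-emergent behavior as any post-baseline behavior with none in the same look-back.
3. Add a shift table by arm from maximum baseline category to maximum post-baseline category.
4. Keep the present count as a separate line, labelled as any post-baseline ideation or behavior, so that no recurrence is lost.

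The cost is a few sentences of SAP text and one shift table. No new data should be needed, provided the pre-treatment C-SSRS records recent recall separately from lifetime history; the public text does not show the form, so this should be confirmed. If the SAP can no longer be amended, the added definition and table can be described in the clinical study report, where SAP 4.1 places adjustments to planned analyses.
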